# 8.4.2 Collection, Recording and Reporting of Serious Adverse Events

# **SAE** Reporting by the Investigator

All SAEs must be reported **immediately** to Ferring Pharmacovigilance as soon as it becomes known to the investigator but not later than within 24 hours of his/her knowledge of the occurrence of an SAE.

The investigator is responsible for submitting the completed SAE Report Form with the fullest possible details within 3 calendar days of his/her knowledge of the SAE.

The SAE Report Form is available in the investigator's file. The SAE report form should be completed in accordance with the instructions provided on the form and sent to Ferring Pharmacovigilance using the contact details below.

Pharmacovigilance, Ferring Pharmaceuticals Inc.

Copies from CRFs regarding demographics, AEs, medical history, and concomitant medication are **mandatory** for initial reports and for follow-up reports if any changes have been made since the initial report.

Additional information relevant to the SAE, such as hospital records, results from investigations, e.g., laboratory parameters, invasive procedures, scans and x-rays, and autopsy results can be faxed or scanned and e-mailed to Ferring Pharmacovigilance using the contact details in the section above. In any case, this information must be supplied by the investigator upon request from Ferring. On any copies provided, such details such as subject's name, address, and hospital ID number should be concealed and instead subject number should be provided.

The investigator will supply Ferring and the IRB with any additional requested information such as results of post-mortem examinations and hospital records.

# **Expedited Reporting by Ferring**

Ferring will report all AEs that are **serious**, **unexpected**, **and with a reasonable possible causality to the IMP**, as judged by either the investigator or Ferring, to the relevant parties within the stipulated timelines.

Serious AEs will be considered reportable regardless of whether or not the IMP was used in accordance with the provisions in the protocol, Investigator's Brochure, and labeling.

# 8.5 Follow-up of Adverse Events and Serious Adverse Events

## 8.5.1 Follow-up of Adverse Events with Onset during the Trial

During the trial, the investigator must follow-up on each AE until it is resolved or until the medical condition of the subject is stable.

Trial Code: 000103 Date: 28-Jul-2014 E-Protocol Amendment-18395; Ver. 5

> Supersedes: 4 Page 44 of 65

After the subject's last visit, the investigator must follow-up on any AE classified as serious or considered to have a reasonable possible causality to the IMP until it is resolved or until the medical condition of the subject is stable. All such relevant follow-up information must be reported to Ferring. If the event is a chronic condition, the investigator and Ferring may agree that further follow-up is not required.

# 8.5.2 Collection of Serious Adverse Events with Onset after Last Trial Visit

If an investigator becomes aware of an SAE after the subject's last visit, and he/she assesses the SAE to have a reasonable possible causality to the IMP, the case will have to be reported to Ferring, regardless how long after the end of the trial this takes place.

Trial Code: 000103 Date: 28-Jul-2014 E-Protocol Amendment-18395; Ver. 5

> Supersedes: 4 Page 45 of 65

# 9 STATISTICAL METHODS

Details of the statistical methodology will be provided in a separate Statistical Analysis Plan. All tabulations will be done by treatment arm. All individual patient data will be listed by domain.

# 9.1 Determination of Sample Size

A total of at least 45 subjects will be exposed to Prepopik. In the two Phase 3 studies for adults, 83% and 84.2% of subjects were classified as success after bowel preparation with Prepopik. With 45 subjects, if 80% of subjects are classified as success in this study, the exact 95% confidence interval of the success rate will be calculated as 65% - 90%.

# 9.2 Subject Disposition

All subjects screened and randomized will be accounted for. All post-randomization discontinuations will be summarized by time of, and reason for, discontinuation and presentation by category will present the frequency and corresponding percentages. The number of subjects screened and not randomized will be presented with the main reason for their non-inclusion.

## 9.3 Protocol Deviations

Major or minor protocol deviations will be defined and documented prior to database lock.

# 9.4 Analysis Sets

All randomized subjects who received any study drug will be included in one or more of the following analysis datasets.

# 9.4.1 Intention-to-Treat (ITT) Dataset

The ITT Dataset will include all subjects who are randomized independent of whether or not the subject receives study treatment dose. Subjects who do not have an efficacy assessment for the data (Aronchick Scale) will be scored as a non-responder. Analyses for the ITT will be conducted according to the randomized treatment.

# 9.4.2 Per Protocol (PP) Dataset

Subjects with major protocol deviations will be excluded from the PP (per-protocol) Analysis Set. Subjects not taking the study medication in the prescribed time intervals will be excluded from the PP analysis set. These subjects will be identified prior to breaking the study blind.

# 9.4.3 Safety Dataset

All subjects consuming at least one dose of study medication will be included in the Safety Analysis Set. Analyses for the Safety Dataset will be conducted according to the treatment actually received.

Trial Code: 000103 Date: 28-Jul-2014 E-Protocol Amendment-18395; Ver. 5

Supersedes: 4
Page 46 of 65

# 9.5 Trial Population

# 9.5.1 Demographics and other Baseline Characteristics

Descriptive statistics of demographics, and other baseline characteristics will be presented by treatment group for the ITT, PP and safety populations. For quantitative variables, all summaries will include the sample size, mean, median, standard deviation, minimum, and maximum. For the qualitative variables, the summaries will include the number and percentage of subjects for each outcome.

# 9.5.2 Medical History, Concomitant Medication and Other Safety Evaluations

Medical history, concomitant medications and the physical examination results will be summarized and listed by subject and any abnormalities noted on the listings.

# 9.6 Endpoint Assessments

## 9.6.1 General Considerations

Nominal p-values and confidence intervals will be presented to aid in interpretation of the summary of data.

Qualitative data will be summarized by presenting the total number of subjects, frequency and percentages within categories by treatment group. The quantitative data will be summarized by presenting the number of subjects, the mean and standard deviation, median, minimum and maximum by treatment group.

# 9.6.2 Primary Efficacy Endpoint

The primary efficacy endpoint will be the proportion of subjects classified as success defined by excellent or good in the Aronchick scale. The primary efficacy analysis will be based on the ITT dataset.

The proportion will be presented by treatment group within each age group, for all Prepopik 1 sachet groups combined, for all Prepopik groups combined, and all standard of care groups combined with the 95% confidence interval.

The treatment group difference will be assessed by constructing the 95% confidence interval of the difference in proportion between each Prepopik group and standard of care within each age group, all Prepopik 1 sachet groups combined and all standard of care groups combined, and all Prepopik groups combined and all standard of care groups combined.

The analyses will be conducted for the PP populations as well.

Trial Code: 000103 Date: 28-Jul-2014 E-Protocol Amendment-18395; Ver. 5

> Supersedes: 4 Page 47 of 65

# 9.6.3 Secondary Endpoint(s)

The following secondary endpoints will be summarized in the same manner as the primary endpoint: proportion of subjects who completed colon cleansing, proportion of subject who record treatment as tolerable or better and proportion who rate treatment as satisfactory as provided on the Tolerability and Satisfaction Questionnaire, and proportion of subjects who completed colonoscopy procedure.

# 9.7 Extent of Exposure and Treatment Compliance

The total study treatment exposure will be summarized and listed by study treatment group for the Safety Analysis Set.

The number and proportion of subjects deviating from the treatment regimen will be tabulated by age and treatment group. The amount of study drug consumed and the timing of treatment administration for each subject according to the instructions will be presented in a data listing.

# 9.8 Safety

## 9.8.1 General Considerations

The safety analysis will include all randomized and dosed subjects, i.e., the Safety Analysis Set. Complete listings and summary tables for all safety information, including AEs, clinical laboratory vital signs, and physical examination, data will be included in the final report.

#### 9.8.2 Adverse Events

All AEs will be coded by the most current version of MedRA (Medical Dictionary for Regulatory Activities) for system organ class and preferred term.

All AEs will be listed by subject, and the incidence of treatment-emergent AEs will be presented by treatment group, causality (relationship to the study medication), and intensity (severity). Deaths, SAEs, and AEs leading to discontinuation will be listed.

# 9.8.3 Safety Laboratory Variables

All clinical laboratory values outside normal range will be listed separately by subject number, including demographic information and flagging values.

Continuous clinical laboratory safety data will be summarized by treatment group and nominal time point (V1 and V3 pre and post colonoscopy) using descriptive statistics: sample size, mean, median, standard deviation, minimum, and maximum values. Changes from pre-treatment will be summarized in the same way.

Categorical clinical laboratory safety data will be summarized by treatment group and nominal time point using the number and percentage of subjects in each category.

Trial Code: 000103 Date: 28-Jul-2014 E-Protocol Amendment-18395; Ver. 5

Supersedes: 4 Page 48 of 65

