On the day before the procedure (24 hours prior), all subjects will be limited to a liquid diet only. Special meal instructions for diabetic subjects are provided in APPENDIX 2. The coordinator who dispenses the drug will instruct the subject and his/her parent/guardian about the exact requirements during the Randomization Visit (Visit 2). Subjects will return to the site 5 (±2) days following their colonoscopy for a laboratory sample (chemistry and hematology). Subjects/parents or guardians will have a telephone assessment on Day 28 after the colonoscopy procedure.

Efficacy of the 2 tested preparations will be evaluated by a blinded endoscopist using the Aronchick scale for overall colon cleansing. A standardized subject questionnaire administered on the day of colonoscopy and prior to sedation and the procedure will assess tolerability and satisfaction of the product.

Pharmacokinetic assessments will be performed on a subset of subjects (10 subjects ages 9 years to 12 years; 5 subjects ages 13 years to 16 years). Assessments will consist of baseline and in the  $\sim$  times of  $C_{max}$  after the various analytes (time based on PK assessment of healthy volunteers).

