Additionally, clinical laboratory evaluation confirmed the safety of Prepopik in phase 3 studies. Bowel preparations can cause considerable dehydration, particularly in patient sub-populations such as the elderly or children, or those with cardiac disease or renal failure, and the resulting hemodynamic changes can prove hazardous to frail patients. Clinically insignificant changes in laboratory values consistent with expected shifts in fluid status as a result of the colon cleansing procedure tended to be greater following dosing with Prepopik compared with HalfLytely in the phase 3 studies, but shifts in these parameters resolved, and results were generally comparable between the treatment groups within 24-48 hours after the procedure. Adequate hydration should be maintained in all subjects during dosing with Prepopik to prevent electrolyte deficiencies such as hyponatremia or hypokalemia. The emphasis on additional fluid consumption in the dosage and administration of Prepopik aids in alleviating this risk.

The magnesium component of the Prepopik product led to transient increased magnesium levels in adult subjects following dosing in the phase 3 studies; however, the levels returned to baseline within 24-48 hours after the procedure without sequelae.

Assessments of vital signs and centralized evaluation of electrocardiogram (3000 ECGs) data from the phase 3 studies showed no signal for Prepopik on any cardiac electro-physiological functions.

> Supersedes: 4 Page 17 of 65

Based on the worldwide safety data reported during the period covered by the periodic safety update reports (01 June 1990 – 31 December 2010), the overall benefit-risk profile of Prepopik remains favorable. Review of literature has revealed no important new safety findings. The safety profile of Prepopik is broadly consistent with the known risks as reported in the most current Summary of Product Characteristics for Prepopik. Predictably, cumulative safety data indicate that, overall, gastrointestinal disorders were the most commonly reported type of reaction, including vomiting, diarrhea, nausea, and abdominal pain. No novel or unexpected AEs were recorded in the adult registration trials.

A summary of the benefits and risks of Prepopik is provided in Table 1-1. Prepopik offers a significant improvement over other currently marketed products in the US, with an ideal balance of efficacy, safety and tolerability for cleansing of the colon as a preparation for colonoscopy.

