### 7.2.3 Clinical Laboratory Variables

All laboratory measurements will be performed using appropriately validated methods by the study site's local laboratory. All sites should follow their local regulations for sample handling and storage.

Laboratory values will be reported to the investigator and sponsor (or the sponsor's representative) and will be entered into the eCRF database, which will be maintained by a clinical research organization selected by the Sponsor.

Out-of-range values will be described in the reference ranges to be provided by the local laboratory. Investigators will assess all out of range values as being either clinically significant or not clinically significant via the eCRF.

Sites will be specially instructed to review all laboratory results in order to determine if the subject is eligible for study participation, and to determine any AEs post study drug administration.

Samples will be collected during Visits 1, 3 and 4 for determination of the following test values:

- Hematology panel:
  - o Full complete blood count and differential
- Coagulation panel:
  - o Prothrombin time, activated partial thromboplastin time
- Full chemistry panel:
  - o Calculated creatinine clearance
  - o Serum magnesium (Mg++)
  - o Serum chemistry: glucose, blood urea nitrogen, potassium, sodium, chloride, calcium, total protein, albumin, total bilirubin, alkaline phosphatase, aspartate aminotransferase, alanine aminotransferase, bicarbonate and gamma glutamyl transferase
- Urinalysis panel

In addition, urine pregnancy tests will be performed at the local laboratory for female subjects of childbearing potential at Visits 1 and 2.

Trial Code: 000103 Date: 28-Jul-2014

E-Protocol Amendment-18395; Ver. 5

Supersedes: 4 Page 37 of 65

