10.3.2 Laboratory Variable Changes Relative to Normal Range

Changes relative to normal ranges will be presented with shift tables showing the total number of subjects, and number and percentage of subjects who experienced a shift from baseline. The following categories for shift tables are defined:

- Low: Values which are below the lower reference range limit;
- Normal: Values which are within the lower and upper reference range;
- High: Values which are above the upper reference range limit.

For all haematology and clinical chemistry variables, shift tables will be prepared to compare baseline values to the worst post-treatment value.

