10.5 Physical Examination

The number and percentage of subjects having an abnormal physical exam at Screening, or with a change from Screening, will be summarized by body system for each treatment group, overall and by age group.

Physical examination findings at each evaluation will be listed for the safety dataset. Subjects with abnormal findings will be noted on the data listings.

11 Interim Analyses

No interim analyses are planned for this study.

12 Deviations from Protocol Analysis

The following are a list of changes and/or additions from the protocol specified analyses:

- In addition to the pre-specified 95% CIs, 90% CIs will also be computed and displayed.
- Additional summaries for pre-specified orthostatic changes in blood pressure will be provided.
- Pharmacokinetic concentration summaries and listings will be provided.

13 References

[1] Clinical Practice Guideline: Orthostatic vital sings full version. Emergency Nurses Association. December 2011.

14 Tables, Listings and Figures

The document with tables, listings, and figures (TLF) shells is presented in a separate document.

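### Protocol 9.8.3 promises categorical laboratory results by time point, but the SAP's categorical tables have no visit dimension, so the timing and resolution of abnormalities are not counted

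*Protocol*

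**What the plan says.** Protocol 9.8.3 treats continuous and categorical laboratory results separately. For the second kind, "Categorical clinical laboratory safety data will be summarized by treatment group and nominal time point", as numbers and percentages of subjects per category. The time points it names, in the sentence on continuous data, are "nominal time point (V1 and V3 pre and post colonoscopy".

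On sampling, protocol 7.2.3 states: "Samples will be collected during Visits 1, 3 and 4 for determination of the following test values". The panels are haematology, coagulation, chemistry (including serum magnesium) and urinalysis. Protocol 6.3 places the Visit 3 sample before the colonoscopy. The Synopsis has subjects return 5 (±2) "days following their colonoscopy for a laboratory sample (chemistry and hematology"; protocol 3.1, 6.4 and Table 6-1 add coagulation at that visit.

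In the SAP, 10.3.1 summarizes numeric values and changes at each nominal time point. Section 10.3.2 defines Low, Normal and High and then says: "For all haematology and clinical chemistry variables, shift tables will be prepared to compare baseline values to the worst post-treatment value". Section 10.3.3 counts subjects with a normal baseline who have at least one markedly abnormal value at any point, using the limits in Appendix 1. Section 10.3.4 is a subject listing of out-of-range values. Section 12 is introduced with "The following are a list of changes and/or additions from the protocol specified analyses" and has three entries: 90% confidence intervals, orthostatic summaries, and pharmacokinetic concentration summaries.

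**The concern.** Abnormal laboratory findings are part of a secondary endpoint, and protocol 1.3 says which question matters. In the adult Phase 3 studies fluid-related changes occurred, but "shifts in these parameters resolved, and results were generally comparable between the treatment groups within 24-48 hours after the procedure", and magnesium returned to baseline over the same interval. The paediatric sampling suits a check of that pattern, with one sample soon after the preparation and one several days later.

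If the only counts are of the worst or any-time value, the report can say how many children in an arm left the reference range. It cannot say how many were out of range just before the procedure, or how many were back in range by Visit 4. A child whose low sodium resolved and a child whose low sodium persisted fall in the same cell. A Visit 4 abnormality due to underlying disease or care after the procedure could also be tabulated together with an effect of the preparation.

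**Working it through.** No figure in the plan bears on this point, so there is none to reproduce. The check compares the texts and then uses a small constructed example.

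**1. What the SAP produces for laboratory data**

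| SAP section | Type of output | By visit? | Panels |
|---|---|---|---|
| 10.3.1 | Numeric summaries of value and change | Yes | Laboratory variables, numeric |
| 10.3.2 | Low/Normal/High shift to worst value | No | Haematology, chemistry |
| 10.3.3 | Count markedly abnormal, normal baseline | No | Variables with limits in Appendix 1, including PT and APTT |
| 10.3.4 | Listing of out-of-range values | Listing, not a count | All |

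No row is both categorical and by visit, which is what protocol 9.8.3 describes. None of the three entries in SAP section 12 covers the omission. Urinalysis has no categorical summary in SAP 10.3. Serum magnesium has no row in Appendix 1 as it reads in the text available, so the worst-value shift appears to be its only categorical count.

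**2. What the worst-value table can distinguish**

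Assumed data: one arm of 15 (the planned size in protocol Table 3-1), all normal at baseline, 5 with a high value after dosing. 'Worst' is High if either visit is High.

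| Course | Worst value | Visit 3 | Visit 4 |
|---|---|---|---|
| High at Visit 3, resolved | 5/15 (33%) | 5/15 | 0/15 |
| High at Visit 3, persisting | 5/15 (33%) | 5/15 | 5/15 |
| High at Visit 4 only | 5/15 (33%) | 0/15 | 5/15 |

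The worst-value column is the same in all three rows, and the by-visit columns separate them. All 5 children are recorded as normal-to-high shifts in every row, so new abnormality is captured. Timing and resolution are not.

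**3. Direction of 'worst'**

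Appendix 1 gives both a low and a high limit for sodium, potassium and glucose. SAP 10.3.2 does not say which value is worst if a child is low at one visit and high at the other. One cell per child cannot hold both.

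**4. Which visits count as post-treatment**

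SAP 10.3.2 names no visits. SAP 10.3 ends the treatment-emergent window when residual drug effect ends, with no length in days. There are two cases:

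- If Visit 4 is inside the window, Visits 3 and 4 are merged, as in step 2.
- If Visit 4 is outside it, no categorical table uses the later sample and resolution is not tabulated at all.

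The counts of interest are missing in either case.

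**5. The time points themselves**

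The list in protocol 9.8.3 leaves out Visit 4 and implies a laboratory sample after colonoscopy at Visit 3. Protocol 6.3 lists only adverse events and orthostatic vital signs after the procedure. The list does not match sampling at Visits 1, 3 and 4.

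**The case against.** The strongest defence is that the categorical sentence in 9.8.3 covers only results that are categorical by nature, such as qualitative urinalysis. Sodium, potassium and glucose would then be continuous, and the shift table would be an SAP addition that replaces nothing. This has weight, because 9.8.3 mentions neither Low/Normal/High grading nor Visit 4. A reader might infer that the protocol already requires graded shifts at Visit 4; its text does not go that far. Even on the narrow reading, though, the SAP specifies no by-visit table for urinalysis and does not declare the gap.

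The second defence is that the time course survives elsewhere. SAP 10.3.1 gives minimum and maximum at each time point. The listing in 10.3.4 is readable at about 15 per arm. Clinically significant abnormalities become adverse events, with onset dated to the sample and an outcome recorded (protocol 8.1 and 8.2.2). All of this stands, but none of it gives a count by arm of children who crossed a limit and then recovered.

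Third, the table shells are a separate document, not available here, and may include by-visit tables. That is possible. The SAP text should still call for them.

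A reader might also infer that pooling two visits distorts the arm comparison by inflating chance findings. With a 95% reference range and two independent visits, the chance of at least one out-of-range value is 1 − 0.95² = 9.75%, against 5% at one visit. That applies equally to every arm, and separate visit tables would spread the same chance findings over two tables. It is not an argument for the change.

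**Conclusion.** The point holds in a limited form. On its plain reading, protocol 9.8.3 promises categorical laboratory results by time point. The SAP text provides none, and section 12 does not say so. What is lost is a count by arm of when abnormalities occurred and whether they resolved, together with a defined direction for 'worst'.

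Three stronger readings are not supported:

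- That new abnormalities go uncounted. The shift is from baseline, and 10.3.3 is restricted to children with a normal baseline.
- That coagulation has no categorical summary. PT and APTT have limits in Appendix 1 and so enter 10.3.3, though not by visit.
- That the SAP expressly merges Visits 3 and 4. This is an inference from undefined terms.

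The 5/15 example rests on assumed data and shows only what the table cannot distinguish. It predicts nothing about this trial. The study is descriptive, with about 75 children and no laboratory hypothesis, so the primary result is unaffected. The gap should still be closed, because resolution of laboratory shifts is the claim in protocol 1.3 that these samples could check.

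**What to change.** - In SAP 10.3.2, add Low/Normal/High shift-from-baseline tables at Visit 3 and at Visit 4 separately, by treatment and age group, and include coagulation.
- Tabulate categorical urinalysis results by visit.
- Keep the worst-value shift as a supplement, split into worst-low and worst-high.
- Define 'post-treatment' by visit, and say whether Visit 4 falls inside the window used in 10.3.2 and 10.3.3.
- Reconcile the nominal time points in protocol 9.8.3 with sampling at Visits 1, 3 and 4, and settle whether coagulation is drawn at Visit 4, since the Synopsis and protocol 3.5.7 omit it.
- If by-visit categorical tables are not wanted, declare and justify that in SAP section 12.

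The cost is SAP wording and a few more tables, with no new data. Cells will be small: at 15 per arm one child is 1/15 = 6.7%, so the tables should be read as descriptive counts.
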